### **1.4 Data Safety Monitoring Board (DSMB)**

Ensuring the ethical conduct of the trial and protecting the rights and welfare of the patients are the tasks of the DSMB.

The DSMB consists of five international clinical experts on epidemiology, stroke, and intracranial aneurysms, who are not involved in the conduct of the trial. The task of the DSMB is to oversee the safety of the trial subjects in the clinical trial by periodically assessing the safety and efficacy of the trial therapy, and to monitor the integrity and validity of the data collected and the conduct of the clinical trial in accordance to CHMP/EWP/5872/03 Corr (EMA 2005). Since interim analyses

are planned, an external biometrician is involved in the DSMB. The DSMB will meet on a regular basis. The exact timing will be scheduled by the DSMB. After reviewing the data on the study conduct (recruitment, protocol adherence/ protocol deviations) and on safety issues the DSMB provides the sponsor with recommendations with regard to continuing the trial (e.g. termination, continuation, or modification) based on the data collected. The data necessary for the DSMB to fulfil this function are provided by the sponsor as determined by the DSMB. Amongst other datasets, these must include listings providing information on serious adverse events and further variables that the DSMB considers necessary and when formal interim analyses are conducted. The DSMB may define stopping rules in addition to the rule described in chapter 9.4 (page 46) and inform the coordinating investigator about which data and which documents (e.g. monitoring plan) need to be provided at which time schedule (e.g. annually, twice per year etc.).

### 1.5 Steering Committee (SC)

The steering committee is comprised of the coordinating investigators and their supporting co-investigators, clinical experts not directly involved in the clinical trial, and the responsible biometrician. The steering committee is responsible for the scientific integrity of the study protocol, the quality of the study conduct as well as for the quality of the final study report. The Steering committee will decide on the recommendations made by the DSMB.

## 2 TRIAL OBJECTIVES AND ENDPOINTS

### 2.1 Primary Objective and Primary Endpoint

The main purpose of this study is to assess the hypothesis that a strategy with a daily intake of low-dose ASA (81mg/day - 100 mg/day) and intensive blood pressure treatment (targeted systolic blood pressure below 120mmHg) with advice to patients to do weekly measurements using a home blood pressure measuring device reduces the risk of aneurysm rupture or growth compared with standard care (i.e. no ASA, blood pressure management according to guidelines which usually advise treatment if systolic blood pressure exceeds 140mmHg, and no home device for weekly blood pressure measuring).

The primary outcome measure will be aneurysm rupture or growth on serial imaging (MR- or CT-angiography). Aneurysm growth is defined as an increase in any aneurysm diameter by  $\geq 1$ mm within  $36\pm 6$  months from randomization. Aneurysm rupture or growth will be assessed centrally by two independent trial radiologists, who will be blinded to the treatment allocation. Events suspicious for SAH but negative CT-imaging will be reviewed centrally by the adjudication committee. Instances of sudden death of patients who died before reaching a hospital will be reviewed centrally by one neurosurgeon and two neurologists who are blinded to the treatment allocation to assess the (un)likelihood of SAH as cause of the sudden death.

### 2.2 Secondary Objectives and Secondary Endpoints

Secondary objectives of the study are:

- A) To assess whether ASA reduces the risk of aneurysm rupture or growth compared with no ASA treatment.
- B) To assess whether intensive blood pressure lowering therapy reduces the risk of aneurysm rupture or growth compared with no intensive blood pressure lowering therapy.

- C) To assess whether intensive blood pressure treatment plus ASA reduces the incidence of cardiovascular events compared with standard BP treatment alone.
- D) To assess whether beneficial effects of the intervention with intensive blood pressure treatment and ASA are not negated by side effects of the intervention.
- E) To assess the effect of the intervention on quality of life
- F) To investigate if the intervention is cost-effective

Secondary endpoints of the study are:

1. Any growth or rupture of aneurysm during follow-up irrespective of the duration of trial participation
2. Difference of aneurysm volume (defined as increase of aneurysm volume in computerized measurements from source images by >10% and >3mm^3) or aneurysm shape (e.g. development of daughter sac)
3. Development of de novo aneurysm on serial imaging
4. If a second aneurysm is present: Growth in diameter or volume and alteration of shape of this second aneurysm.
5. Clipping/coiling during the study period
6. Any ischemic or haemorrhagic stroke, defined as clinical symptoms of stroke AND a compatible lesion on imaging
7. Myocardial infarction defined as increase of Troponin, CKMB and/or presence of new significant Q waves obtained in ECG
8. Vascular death (including fatal stroke, fatal myocardial infarction, sudden death)
9. Death from all other causes
10. Major spontaneous bleeding requiring hospitalisation defined as substantially disabling bleeding, intraocular bleeding leading to the loss of vision, or bleeding necessitating the transfusion of at least 2 units of erythrocyte concentrates
11. Blood pressure; any data on blood pressure management used
12. Safety aspects (adverse and serious adverse events, including those mentioned above, see also 8.1.6 and 8.2)
13. Quality of life (as determined by completion of the paper-based EQ-5D-5L form by patient)

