#### Cardiovascular benefits:

A meta-analysis on randomized controlled trials of ASA therapy in participants without cardiovascular disease that reported data on myocardial infarction (MI), stroke, and cardiovascular mortality trials identified six major prospective trials with a total of 95,456 individuals: 3 trials included only men, 1 included only women, and 2 included both sexes. Based on the absolute risk reduction of 0.30% in men and 0.37% in women, the number needed to treat to prevent one cardiovascular event over the mean follow-up of 6.4 years was 333 women and 270 men. In other words, ASA therapy for an average of 6.4 years results in an average absolute benefit of approximately 3 cardiovascular events prevented per 1000 women and 4 cardiovascular events prevented per 1000 men. Of note, the population studied had a low risk of fatal or nonfatal vascular events. It has been shown that the cardioprotective benefit of ASA is related to the cardiovascular risk in the population studied. As a result, the absolute risk reduction for these events was small. In women, ASA therapy was associated with a 17% reduction in the odds of stroke (OR 0.83; 95% CI 0.70-0.97). With respect to stroke subtypes in women, ASA was associated with a 24% reduction in ischemic stroke (OR 0.76; 95% CI 0.63-0.93), but had no effect on hemorrhagic stroke (OR 1.07; 95% CI 0.42-2.69). In men with ASA, the odds ratio for stroke was 1.13; 95% CI 0.96-1.33. With respect to stroke subtypes in men, ASA had no effect on ischemic stroke (OR 1.00; 95% CI 0.72-1.41), but was associated with an increased risk of hemorrhagic stroke (OR 1.69; 95% CI 1.04-2.73). The risk of MI was significantly reduced in men (and not in women) receiving ASA, corresponding to an average absolute benefit of approximately 8 MI events prevented per 1000 men treated for 6.4 years. In addition to cardiovascular effects, long term ASA use is likely to prevent cancer.

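### Two secondary endpoint definitions misclassify events if followed as written: major bleeding has no fatal or intracranial criterion, and a biomarker rise alone counts as myocardial infarction

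*Protocol*

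**What the plan says.** Section 2.2 lists the secondary endpoints. Section 7.2 repeats the list, and the Synopsis and the analysis variables in Section 9.1 give the same definitions for the items at issue.

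- Endpoint 10 reads: "Major spontaneous bleeding requiring hospitalisation defined as substantially disabling bleeding, intraocular bleeding leading to the loss of vision, or bleeding necessitating the transfusion of". The transfusion threshold is 2 units or more. This is the only endpoint dedicated to bleeding.
- Endpoint 7: "Myocardial infarction defined as increase of Troponin, CKMB and/or presence of new significant Q waves obtained in ECG".
- Endpoint 6, for comparison: "Any ischemic or haemorrhagic stroke, defined as clinical symptoms of stroke AND a compatible lesion on imaging".
- Endpoint 8: "Vascular death (including fatal stroke, fatal myocardial infarction, sudden death"), followed by endpoint 9: "Death from all other causes".
- Endpoint 12: "Safety aspects (adverse and serious adverse events, including those mentioned above, see also 8.1.6 and 8.2").

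Two secondary objectives depend on these items. Objective C concerns cardiovascular events. Objective D is: "To assess whether beneficial effects of the intervention with intensive blood pressure treatment and ASA are not negated by side effects of the intervention". No composite or weighting of benefit against harm is defined, so the separate endpoints have to carry that judgement.

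**The concern.** Section 1.3 names major, mainly gastrointestinal, bleeding as the extracranial risk of ASA. The endpoint meant to measure it grades severity by disability, blindness or transfusion need, and makes hospitalisation a condition. A bleed can be as severe as possible and still miss all of these, because death is not a criterion. An intracranial bleed with a good recovery misses them too.

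For infarction the problem runs the other way. Troponin, CKMB and Q waves are joined by and/or, with no threshold, symptom or other sign of ischaemia required. Stage III kidney disease is eligible: Section 4.5 excludes only stages IV and V, and Section 6.3 plans for stage III patients. That troponin can rise in such patients without infarction is general clinical knowledge. The protocol gives no frequency for it.

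The written definitions matter more here because the trial is open-label. Section 2.1 provides blinded or central review for rupture, growth, suspected SAH with negative CT, and sudden death before reaching hospital. Section 9.3 sends unclear endpoints to a committee. No routine blinded review of infarction or bleeding is stated.

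**Working it through.** **The plan's own figure.** The protocol gives no calculation for these endpoints. Its one design calculation is in Section 9.1: 15% versus 8.25%, alpha 0.05 (two-sided assumed), power 80%. With pooled variance:

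n = [1.96 × √(2 × 0.11625 × 0.88375) + 0.8416 × √(0.15 × 0.85 + 0.0825 × 0.9175)]² / 0.0675² = 353 per group.

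This matches the stated 353, and nothing below changes it.

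**Literal test of endpoint 10**

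| Event | Counted as major bleeding? | Where else recorded |
|---|---|---|
| Fatal GI bleed, admitted, at least 2 units needed | Yes | 8 or 9; 12 |
| Same, but death before the units are given | Yes; the text asks that transfusion be necessitated, not completed | 8 or 9; 12 |
| Fatal bleed, death before admission | No, if hospitalisation is read as having occurred | 8 or 9; 12 |
| Symptomatic intracranial haemorrhage with imaging lesion, not disabling, not transfused | No | 6; 12 |
| Aneurysmal SAH, not disabling, not transfused | No | Primary endpoint; 12; expedited notice (Section 9.4); also 6, since Section 1.1 classes SAH as stroke |

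The third and fourth rows are the gap. For the third row, the protocol also does not settle whether the death belongs to endpoint 8 or 9. The components named in endpoint 8 do not mention bleeding, but the list is introduced by the word including and is therefore open.

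**Literal test of endpoint 7.** Take a patient with a small troponin rise, no symptoms and no ECG change. The and/or link makes this an infarction. Under endpoint 6, symptoms without a lesion, or a lesion without symptoms, are not a stroke. The same list therefore demands corroboration for stroke and none for infarction.

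**How many bleeds to expect.** Section 1.3 gives an absolute increase in major bleeding over 6.4 years of 0.25% in women and 0.33% in men. Section 4.1 gives 388 patients per group. Linear scaling to 3 years is an assumption.

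- Women's figure: 0.25% × 3/6.4 = 0.117%; × 388 = 0.45 events
- Men's figure: 0.33% × 3/6.4 = 0.155%; × 388 = 0.60 events

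Treatment can run to 120 months (Section 3.2). If all 388 were treated that long, the figures would be 0.25% × 10/6.4 × 388 = 1.5 and 0.33% × 10/6.4 × 388 = 2.0.

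These are excesses of all major bleeds. They show that the endpoint will have few events, so that one reclassified bleed is larger than the expected 3-year excess. They do not measure how many bleeds would be misclassified.

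**The case against.** The strongest reply is that nothing is lost. Deaths fall under endpoint 8 or 9, symptomatic intracranial bleeds with a lesion under endpoint 6, and all of them under endpoint 12, since death, threat to life and hospitalisation are SAE criteria (Section 8.1.2). That stands, and it limits the point to classification. It does not remove it, because a reader comparing major bleeding between arms will look at endpoint 10. Endpoint 12 is also a doubtful fallback for that comparison. Section 9.2 limits the safety set to patients who received study medication, and Section 5.4.2 gives it only to the intervention group.

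The omitted events may also be very rare. Section 1.3 cites five fatal gastrointestinal haemorrhages among 39,876 women over 10 years: 5/39,876 = 0.0125%, or about 0.1 event in 776 patients. This is fair, although that trial used alternate-day dosing in healthy women and the figure excludes intracranial bleeds.

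For infarction, the protocol schedules no troponin, and Section 7.1 allows an ECG only when medically imperative. A troponin result will therefore usually follow clinical suspicion. That makes false infarctions fewer, but the wording still admits them.

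A reader might draw three stronger conclusions that the documents do not support.

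- *Every fatal bleed escapes endpoint 10.* Those that are disabling or necessitate 2 units qualify.
- *Pooling stroke types is an error because ASA acts in opposite directions on them.* Section 1.3 says of men that ASA had no effect on ischaemic stroke (OR 1.00) "but was associated with an increased risk of hemorrhagic stroke (OR 1.69; 95% CI 1.04-2.73"). In women it reports ischaemic OR 0.76 and no effect on haemorrhagic stroke (OR 1.07; 95% CI 0.42-2.69). The effects differ, but neither sex shows established opposite ones. Any stroke is a legitimate endpoint. In men the all-stroke interval (0.96-1.33) includes 1 while the haemorrhagic interval does not. That is a reason to suggest reporting by subtype in the SAP, not a fault in the protocol.
- *The trial's statement on the net benefit of ASA will be wrong.* No such measure is defined, and objective D concerns the combined strategy.

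**Conclusion.** The point holds for two definitions. Endpoint 10 leaves out some fatal bleeds and non-disabling, non-transfused intracranial haemorrhages. Endpoint 7 accepts a biomarker rise of any size, alone, as infarction. Both are rules that the protocol itself fixes in four places, so an SAP that follows them would inherit the fault. The protocol also leaves open whether fatal bleeding belongs to endpoint 8 or 9.

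The consequence is limited to secondary endpoints and the reading of objectives C and D. The number of misclassified events cannot be derived from the documents. The expected excess of 0.45 to 0.60 major bleeds over 3 years rests on linear scaling and on carrying the cited meta-analysis over to this population, and shows only that events will be few. The correction is worth making because it is cheap and the trial is open-label.

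**What to change.** Make the same changes in the Synopsis and in Sections 2.2, 7.2 and 9.1.

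- **Endpoint 10:** add any fatal bleeding and any symptomatic intracranial haemorrhage as criteria, without the hospitalisation condition for these two. Show aneurysmal SAH on a separate line, since it is already a primary event.
- **Endpoint 7:** require a biomarker rise together with at least one of symptoms, new ECG changes or imaging evidence of ischaemia. This would also stop new Q waves alone from counting, so that should be a deliberate decision.
- **Endpoints 8 and 9:** state which of the two takes fatal bleeding.

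As a reporting suggestion only, the SAP could tabulate stroke by subtype.

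The cost is a wording amendment, matching eCRF fields, and re-coding of past events from SAE records. Re-coding should be done without knowledge of allocation. Some past biomarker-only infarctions may lack the symptom or ECG detail needed and should then be listed as unclassifiable. The primary analysis, the sample size and patient visits do not change.

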### 2.3 Additional Research

Participants in the intervention group will receive a blood pressure measurement device to perform blood pressure home-measurements, as an additional measure of blood pressure control and to increase compliance, thus quality assurance. At the time of follow-up during the study visits, participants will provide the local investigators of each study site the blood pressure measurement device for download of the blood pressure data onto a tablet. A graph comprising mean systolic and diastolic blood pressure values obtained over the past 6 months will enable the local investigators to assess whether or not study participants have reached their assigned blood pressure target. Additionally, blood pressure data will be transmitted in a pseudonymized fashion via a secure online connection to a central database at the sponsor's institution. The uploaded data may be used for further analysis of achieved blood pressures in the intervention group at the end of the trial. The uploaded data will not be used for a diagnostic or therapeutic intervention if the blood pressure is outside the normal range.

### 3 TRIAL DESIGN AND DESCRIPTION

#### 3.1 Trial design and justification of design aspects

This phase III multicenter, randomised, controlled trial with a PROBE design (prospective, randomised, open-label trial with blinded outcome assessment) is designed to assess whether a strategy with low dose ASA (81 mg/ day - 100mg/day) and intensive blood pressure treatment (targeted systolic blood pressure below 120mmHg) with weekly measurements using a home blood pressure measuring device reduces the risk of intracranial aneurysm rupture or growth, which is an established surrogate for the risk of rupture, compared with standard care (i.e. no ASA and blood pressure management according guidelines, which usually advise treatment if systolic blood pressure exceeds 140mmHg).

We will perform a phase III trial instead of a phase I/II trial since the protective effect of ASA on aneurysm inflammation or rupture was highlighted in a nested case-control study of UIA patients (n=1691) as well as in a small phase I trial randomising patients to ASA treatment or treatment as usual, which showed a significant reduction of radiological and histological aneurysm wall inflammation as surrogates for rupture. Further, the recent SPRINT study randomising 9361 patients to intensive versus standard BP treatment demonstrated a reduction of the primary composite outcome (myocardial infarction, other acute coronary syndromes, stroke, heart failure, or death from cardiovascular causes) without affecting the overall incidence of adverse or serious adverse events.

We chose an open-label design with observer-blinded outcome adjudication (by two independent neuroradiologists), because: a) a double or single-blinded study with predefined blood pressure targets would not be feasible, irrespective of the concomitant ASA treatment, b) to allow inclusion of UIA patients who are already treated for hypertension; and c) for pragmatic reasons, e.g. to not having to unblind treatment allocation for patients, who require a medical procedure potentially under ASA during the duration of the study (for at least 36±6 months after randomization). Also, due to very specific and well-known effects of ASA, it would be very likely to un-blind the patient by side effects.

Because the 5-year risk of rupture is usually <3% in patients with small aneurysms, a randomized trial with rupture as the main primary outcome measure is unfeasible. We therefore combine aneurysm rupture with aneurysm growth as the primary outcome measurement, since UIA growth occurs more often and is a predictor of aneurysm rupture (see also above). The risk of growth is approximately 15% in 3 years, and approximately 18% in 5 years.

From a scientific perspective it would be important to understand the individual protective effects of both factors, i.e. intensive blood pressure reduction and ASA treatment, on aneurysm growth or rupture. We decided on a two-arm trial (i.e. concomitant ASA treatment plus intensive blood pressure treatment) instead of a three-arm trial (i.e. ASA treatment or intensive blood pressure management or standard of care), because in a three-arm trial investigating the protective effect of each component separately, the effect size for each treatment component would be smaller than for the combined effect. Hereby, the number of patients would not only increase as a result of adding an additional arm, but also because the effect size for each component was smaller.

We assume that combined ASA and intensive blood pressure lowering will reduce 3-year incidence of the primary outcome (aneurysm rupture or growth) from 15% to 8.25%, thus a relative risk reduction of 45%. We previously considered a trial with ASA only (without blood pressure reduction). For such a trial we assumed that the risk reduction to be attributed to ASA is 22.5%. Then the reduction by ASA monotherapy would be from 15% to 11.625% and the subsequent number for the a trial with two arms and with such a contrast would be 2 x 1597 for a total of 3194 patients who are available for the analysis. Even if we assume that the risk reduction contributed

|   |   |                               |
|---|---|-------------------------------|
| Clinical Trial Code: Protect-U
EudraCT: 2017-000514-35 | Trial Protocol
Version 07 - August 23 - 2022 | Page 26 of 62
CONFIDENTIAL |
|---|---|-------------------------------|

to ASA would be as large as 30% (15% down to 10.5%) a two-armed trial would require 2 x 864 = 1728 patients. Based on these calculations we decided against such a design.

We also considered a 2 x 2 factorial design (ASA vs. no ASA and intensive vs. regular blood pressure control). Since such a trial would need at least 1,728 patients, we also considered this design unfeasible.

For more details about Randomisation see section 5.5 "Randomisation .

### *Feasibility*

The trial will be performed worldwide in up to 30 medical centers that see at least 50 new patients with unruptured aneurysms per year per center in addition to existing patients with unruptured aneurysms who are already managed conservatively at each center. These patients will be screened for study eligibility. If patients had an MRA or CTA scan 3 months prior to eligibility assessment, they are also eligible.

## **3.2 Trial Duration and Schedule**

The duration of the trial for each subject is expected to be at least 36 months intervention and one-month follow-up. For those subjects enrolled early in the trial, the intervention will be continued until the last subject enrolled completed the 36 months of intervention (maximum duration of treatment 120 months ± 30 days).

The overall duration of the trial is expected to be approximately 162 months. Recruitment of subjects has been started in in Q3 2017 in Germany. The actual overall or recruitment duration may vary. Based on a planned interim analysis, the DSMB can recommend modifying the duration of the trial. The study end is defined as "last patient out" (LPO), this may apply as well to a follow-up visit, if appropriate.

|  |                    |
|--|--------------------|
| Duration of the clinical phase for each patient: | [up to 120 months] |
| Total trial duration:                            | [162 months]       |
| Duration of clinical phase:                      | [144 months]       |
| Beginning of the preparation phase:              | [Q2 2017]          |
| FSI (first subject in):                          | [Q3 2017]          |
| LSI (last subject in):                           | [Q2 2026]          |
| LSO (last subject out):                          | [Q2 2029]          |
| DBL (database lock):                             | [Q3 2029]          |
| Statistical analyses completed:                  | [Q4 2029]          |
| Trial report completed:                          | [Q2 2030]          |

